5.4 Definition of Dose Limiting Toxicity

Toxicity will be evaluated according to the NCI CTCAE version 5.

DLT is defined as any of the following events occurring within the first 2 cycles that are considered by the treating physician to be at least possibly related to therapy with study drug(s). AEs in which the relationship to study drug cannot be ruled out should be considered possibly related to study drugs TAK-659 and/or Ixazomib.

- Prolonged myelosuppression with the persistence of \geq Grade 4 neutropenia or thrombocytopenia in the absence of leukemia (blast count <5% in bone marrow) at least 42 days after the initiation of therapy.
- Any Grade 3 or greater nonhematologic toxicity with the following exceptions:
 - Grade 3 nausea and/or emesis resolved to \leq Grade 1 or baseline in a week after the use of an optimal antiemetic regimen based on standard practice. The optimal antiemetic regimen is defined as an antiemetic regimen that employs both a 5-hydroxytryptamine 3 serotonin (5-HT3) antagonist and a corticosteroid given in standard doses and according to standard schedules. Grade 3 nausea, vomiting must not require tube feeding, total parenteral nutrition, or require prolonged hospitalization.
 - Grade 3 diarrhea that resolved to \leq Grade 1 or baseline in a week after receiving the maximal supportive therapy based on standard practice. Grade 3 diarrhea must not require tube feeding, total parenteral nutrition, or require prolonged hospitalization.
 - Brief (<1 week) Grade 3 fatigue.
 - Electrolyte abnormalities correctable within 72 hours

- Grade 3 or 4 tumor lysis syndrome if it is successfully managed clinically and resolves within 7 days without end-organ damage.
- Failure to administer $\geq 75\%$ of planned doses of the study drug due to TAK-659- or Ixazomib-related or possibly related hematologic (considered not related to leukemic infiltration) or nonhematologic toxicities.
- Other TAK-659- or Ixazomib-related Grade 2 or greater nonhematologic toxicities that, in the opinion of the investigator, require a dose reduction or discontinuation of therapy.
- Confirmed Hy's law/guideline cases of drug-induced liver injury: ALT or AST $>3\times$ upper limit of normal and total bilirubin $>2\times$ ULN, which is not cholestatic (ALT value \div ALT ULN) \div [Alkaline phosphatase value \div Alk phos ULN] $= <2$), and not caused by disease. This will require permanent drug discontinuation.
- Any confirmed grade 4 elevation of a single liver enzyme, even absent bilirubin elevation, will require permanent discontinuation from protocol therapy.

Although DLT-like events may occur at any point during treatment, DLTs defined during Cycles 1-2 of treatment will be given more influence for decisions regarding dose escalation for cohorts, expansion of a dose level, or evaluation of intermediate dose levels for purposes of MTD determination. Patients will be monitored through all cycles of therapy for treatment-related toxicities.

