6.1 Dose Delays/Dose Modifications

All toxicities that occur during the study will be actively managed following the standard of care unless otherwise specified in the protocol.

Patients who have the TAK-659 dose held due to treatment-related or possibly related AEs may resume study drug after resolution of the AE but may either maintain the same dose level or have doses of TAK-659 reduced (dose reduction) by at least 1 dose level. When a dose reduction occurs, the TAK-659 dose will be reduced to the next lower dose that either been established as a safe dose during dose escalation or is lower by a 20-mg increment. If initial dose adjustment does not provide sufficient relief, the dose of TAK- 659 can be further reduced if the treating physician considers that the patient is benefiting from study treatment and may benefit at a further reduced dose of TAK-659. When a dose reduction of TAK-659 is required due to toxicity, no dose re-escalation will be permitted.

If TAK-659 dosing is delayed for > 21 days for TAK-659-related or possibly related toxicities despite supportive treatment per standard clinical practice or more than 2 dose reductions are required in a patient, this patient should be considered to have study treatment discontinued, unless the treating physician considers that the patient may benefit from continued study treatment after resolution of AEs

to \leq Grade 1, or baseline, or a level considered acceptable by the physician. The patient will continue to be followed for 30 days for safety evaluation after the last administration of TAK-659.

Patients who experience a DLT (during escalation) or DLT-like toxicity (during phase 2 of the study) during the first cycle will, in general, require that treatment with TAK-659 be permanently discontinued. If, in the opinion of the investigator it is in the patient's best interest to continue treatment with TAK-659, then the dose of TAK-659 will be reduced by at least 1 dose level when treatment resumes after recovery of the toxicity or toxicities in question to \leq Grade 1 or to baseline values or to a level considered acceptable by the investigator. However, if a patient requires a dose delay of > 21 days for such an event to resolve despite the best supportive care permissible per protocol, then the patient must be discontinued from the study.

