6.1.2 TAK-659 dose modifications for Nonhematologic Toxicities

Please refer to the Table below for dose held and dose reduction recommendations for non-hematologic toxicities. When the dose of TAK-659 is withheld based on the following criteria, clinical and laboratory re-evaluation should be repeated at least weekly or more frequently until the toxicity resolves to \leq Grade 1, or baseline, or a level considered acceptable by the treating investigator (must be \leq Grade 2). Upon recovery, TAK-659 may be reinitiated either at the same dose level or at a reduced dose level. For events in which there are transient lab value abnormalities that, based on investigator assessment, are not clinically significant or related to disease and not the drug, continuation of therapy without following the dose modification guideline is permissible after discussion with the sponsor investigator.

Criteria	Action
All Grade 3 Nonhematologic Toxicities with the exception of:	
 • Hold TAK-659 until resolution to Grade \leq 1 or baseline or a level considered acceptable by the investigator (must be \leq Grade 2). 
 ◦ If resolved in \leq 7 days, then maintain the dose level. ◦ If resolved in $>$ 7 days, then dose reduce by 1 dose level. ◦ If recurs, then dose reduce by 1 dose level. • For the exceptions listed, maintain dose level (no dose hold required). • Permanent discontinuation should be considered if the toxicities persist as \geq Grade 3 for more than 21 days despite temporary disruption of study drug.
Grade 4 Nonhematologic Toxicities	
 • Permanently discontinue TAK-659 for any grade 4 nonhematologic toxicities that are at least possibly related to TAK-659.

In general, the study drug(s) will resume only after the resolution of AEs to \leq Grade 1 or baseline or as specified in these dose modification guidelines. However, retreatment with study drug(s) could start when the AEs are resolved to a level deemed acceptable by the investigator. When a dose reduction of TAK-659 is required, no re-escalation of dose will be permitted.

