New or worsening Grade 1 peripheral neuropathy with pain or Grade 2	
 • Hold study drug until resolution to Grade ≤ 1 or baseline 	Grade 2 signs and symptoms: Moderate symptoms; limiting instrumental activities of daily living (ADL) [27]
New or worsening Grade 2 peripheral neuropathy with pain or Grade 3	
 • Hold study drug until resolution to Grade ≤ 1 or baseline • Reduce study drug to next lower dose upon recovery 	Grade 3 signs and symptoms: severe symptoms; limiting self-care ADL; assistive device indicated [27]
New or worsening Grade 4 peripheral neuropathy	
 • Discontinue study drug 	
Grade 2 Rash	
 • Symptomatic recommendations as per section 6.3 	The investigator and project clinician may discuss considerations for dose modifications and symptom management.
Grade 3 nonhematologic toxicity judged to be related to study drug	
 • Hold study drug until resolution to Grade < 1 or baseline 	Symptomatic recommendations noted in Section 6.3
If not recovered to $<$ Grade 1 or baseline within 4 weeks	
 • Reduce study drug 1 to next lower dose upon return to $<$ Grade 1 or baseline 	
Subsequent recurrence Grade 3 that does not recover to $<$ Grade 1 or baseline within 4 weeks	
 • Hold study drug until resolution to Grade < 1 or baseline • Reduce study drug to next lower dose 	Monitor closely, take appropriate medical precautions, and provide appropriate symptomatic care
Grade 4 nonhematologic toxicities judged to be related to study drug	
 • Consider permanently discontinuing study drug 	Exceptions are cases in which the investigator determines the patient is obtaining a clinical benefit

Once ixazomib is reduced for any toxicity, the dose may not be re-escalated.

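### For a related, confirmed Grade 4 liver enzyme elevation in Cycles 1–2, Section 5.4 stops protocol therapy, but the ixazomib table lets a benefiting patient stay on ixazomib

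*Combined protocol and SAP*

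**What the plan says.** Section 5.4 lists dose-limiting toxicities, described as "events occurring within the first 2 cycles that are considered by the treating physician to be at least possibly related to therapy". One bullet is a treatment instruction: "Any confirmed grade 4 elevation of a single liver enzyme, even absent bilirubin elevation, will require permanent discontinuation from protocol therapy". It names no exception and refers to protocol therapy, not to one drug.

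The dose-modification rules in Section 6 are written drug by drug.

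- **TAK-659 (6.1.2):** "Permanently discontinue TAK-659 for any grade 4 nonhematologic toxicities that are at least possibly related to TAK-659".
- **Ixazomib (second table under 6.1.3, non-hematologic toxicities):** the Grade 4 row is triggered by "Grade 4 nonhematologic toxicities judged to be related to study drug". The action is "Consider permanently discontinuing study drug", and the adjoining column adds: "Exceptions are cases in which the investigator determines the patient is obtaining a clinical benefit". Liver enzymes are not carved out and 5.4 is not mentioned.
- **General retreatment text (end of 6.1.2):** "However, retreatment with study drug(s) could start when the AEs are resolved to a level deemed acceptable by the investigator".
- **First-cycle DLTs (6.1):** TAK-659 is in general stopped, but the investigator may decide otherwise on best-interest grounds. The operative words are: "interest to continue treatment with TAK-659, then the dose of TAK-659 will be reduced by at least 1 dose level when treatment resumes".

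Section 6.4 refers to 6.1 for stops due to toxicity and does not mention 5.4.

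**The concern.** Two rules cover the same safety event and give different answers for one of the two drugs. The stricter rule sits in a definitions section that serves dose escalation. The softer one sits in the table that a site opens when it has to decide whether to give the next ixazomib dose. Nothing in Section 6 sends the reader back to 5.4.

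What is at stake is re-exposure to ixazomib after a severe, confirmed, drug-related liver enzyme elevation, in a combination that has not been given before. Sites could also handle the same event differently. Sample size, error rates and the response analysis are not affected.

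**Working it through.** No arithmetic applies, because the plan attaches no figure to this rule. The check sets the rules side by side and applies them to cases.

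**The two rules**

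| | Section 5.4 bullet | Ixazomib Grade 4 row (6.1.3) |
|---|---|---|
| Event | Confirmed Grade 4 elevation of one liver enzyme | Any Grade 4 non-hematologic toxicity, which includes this one |
| Attribution | At least possibly related to study drug(s) | Judged related to study drug |
| Window | List limited to the first two cycles | None stated |
| Action | Mandatory permanent stop | Stop to be considered |
| Exception | None | Investigator judges that the patient benefits |
| Reach | Protocol therapy, read here as both drugs | Ixazomib |

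**Case 1: Cycles 1–2, related to both drugs, patient judged to benefit.** Under 5.4 both drugs stop permanently. Under Section 6, TAK-659 also stops permanently (6.1.2), but ixazomib may continue or restart. The rules conflict, for ixazomib only.

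**Case 2: Cycles 1–2, related to ixazomib, TAK-659 ruled out.** Under 5.4 both drugs stop. Under Section 6 ixazomib may again continue if the patient benefits, so the same conflict arises. The TAK-659 row is not triggered, so it is silent and does not contradict 5.4.

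**Case 3: Cycles 1–2, attributed to TAK-659 alone.** Under 5.4 both drugs stop. Under 6.1.2 TAK-659 stops. No ixazomib row applies. That is a silence, not a conflict.

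**Case 4: after Cycle 2.** The TAK-659 stop in 6.1.2 still applies, since it has no cycle or phase limit. For ixazomib, the list heading in 5.4 no longer covers the event, although the bullet itself is worded generally. The closing paragraph of 5.4 accepts that similar events can occur later, but deals only with their weight in escalation decisions.

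**Case 5: phase II.** The TAK-659 stop applies as in Case 4. Section 13.2.1 monitors DLTs in phase II without restating the liver stop. Section 6.1 does address DLT-like toxicity in phase II, but only in the first cycle and only for TAK-659. Whether the 5.4 stop reaches ixazomib is not stated.

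**Search for a tie-breaker.** Section 6.4 points to 6.1 only. Section 6.3.13, on enzyme elevations, says that they are usually reversible on interruption and mentions no permanent stop. The best-interest sentence in 6.1 is not made subject to 5.4 or to the TAK-659 Grade 4 row. No sentence gives 5.4 precedence.

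**The case against.** The strongest reply is that the rules can be applied together. The 5.4 sentence is specific and mandatory, while the ixazomib row is generic and permissive. A site that stops both drugs complies with every text, and reading the specific over the general favours 5.4. This is correct, but the protocol does not say so, and the row's benefit exception gives a site a written basis for the opposite choice.

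Three further points narrow the problem without removing it.

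- **TAK-659 would usually stop too.** Section 5.4 counts an event as possibly related when the link to study drug cannot be ruled out. Treatment-related AST and ALT increases were reported in 47% and 26% of patients in the pooled TAK-659 studies (1.4.6), so TAK-659 would rarely be cleared. Continuing would then mean ixazomib alone, which no text in this combination trial affirmatively provides for. The ixazomib row, however, does not make its exception depend on TAK-659 being continued.
- **Delay limits.** Sections 6.1 and 6.2 end treatment after a delay of more than 21 days, and 6.4 after an interruption of 21 days or more. They do not cover a patient who continues or recovers sooner, and one paragraph of 6.1 has a physician exception.
- **Oversight.** Weekly phase I safety calls (14.1) and committee approval of dosing decisions (14.3) make inconsistent handling likely to be noticed. They do not settle which rule applies.

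A reader might infer more than the documents support:

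- *That TAK-659 could also be restarted after such an event.* Its Grade 4 row in 6.1.2 is mandatory and agrees with 5.4. The best-interest sentence in 6.1 is general and is best treated as loose drafting.
- *That the whole stop is uncertain after Cycle 2 and in phase II.* For TAK-659 it is explicit in every cycle and both phases, so only ixazomib is open.
- *That the share of a 12-month course lying beyond Cycle 2 measures the problem.* It counts calendar time, not patients. It also presumes that the list heading limits the rule, which is the point in doubt.

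**Conclusion.** The inconsistency is real but narrow. In Cycles 1–2, one row of the ixazomib table permits what 5.4 forbids, when the event is judged related to ixazomib and the investigator invokes benefit. Separately, the text does not settle whether the ixazomib stop applies after Cycle 2 and in phase II.

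No count of affected patients can be given. The available text reports no Grade 4 liver enzyme rate. In the single-agent TAK-659 AML study (C34002), no DLTs of this kind were seen at 60 or 100 mg, and this trial gives at most 100 mg. The number affected may be zero.

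The conclusion rests on two readings: that protocol therapy means both drugs, and that a liver enzyme elevation counts as a non-hematologic toxicity in the ixazomib table. Neither is strained. The point should be corrected because the rule protects patients and the correction is a matter of wording.

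**What to change.** Add to the ixazomib Grade 4 row:

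> A confirmed Grade 4 elevation of a single liver enzyme that is at least possibly related to study drug(s) requires permanent discontinuation of both TAK-659 and ixazomib under Section 5.4. The clinical-benefit exception does not apply.

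Make the best-interest sentence in 6.1 subject to the same rule. In the same edit, the sponsor should state whether the ixazomib stop also holds after Cycle 2 and in phase II. A cross-reference from 6.4 to 5.4 would be a useful tidy-up. The pneumonitis text in 6.3.4 already names both drugs and can serve as a model.

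**Cost.** There is none in Cycles 1–2, since 5.4 already requires the stop. If the sponsor extends the rule to later cycles, a benefiting patient with such an event loses the option of continuing ixazomib. That is a clinical choice for the sponsor to make openly.

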5.5 Phase II Study

Upon enrollment, the mutational profiles from Foundation One, Mayo, Tempus, Quest, ARUP or an institutional CLIA-certified laboratory will be recorded in the study database with minimum gene coverage as noted in Section 8.3. Subjects will be enrolled into either the FLT-3 mutant cohort or the FLT-3 WT cohort according to their mutation assay results.

5.6 TAK-659 and Ixazomib Administration

Drug	Dose	Route ¹	Schedule ²	Cycle Length
TAK-659	RP2D	PO	Days 1-15	21days
Ixazomib	RP2D	PO	Days 1, 8, 15	

1: Please see details below regarding administration of oral study drugs. On clinic days for PK determination, TAK-659 will be taken first and then Ixazomib. **NOTE:** Patients will be asked to keep a diary of dosing and bring to each clinic visit.

2: A window of ± 3 days may be applied to all study visits to accommodate observed holidays, inclement weather, scheduling conflicts etc. Date and time of each drug administration should be clearly documented in subject's chart and electronic case report forms (eCRFs).

5.6.1 TAK-659 Administration

TAK-659, should be taken on an empty stomach at least 1 hour before and no sooner than 2 hours after ingestion of food and/or beverages other than water. Each tablet should be swallowed separately with a sip of water. A total of approximately 8 ounces (240 mL) of water should be taken with the prescribed doses of TAK-659. Patients must swallow the tablets whole; the tablets must not be chewed, crushed, or manipulated in any way before swallowing.

Patients should be instructed to take their study medication at approximately the same time each day and to not take more than the prescribed dose at any time. If a patient fails to take TAK-659 one day, or if a patient does not take TAK-659 at their scheduled dosing time (\pm 6 hours of the scheduled dosing time), that dose should be skipped, and the patient must not make dose adjustments to account for the missed dose on subsequent days, for example, by taking a double dose of study drug(s) on the following day. Patients should record any skipped doses in their dosing diary (and resume dosing at the next scheduled time with the prescribed dosage).

If severe emesis prevents the patient from taking a TAK-659 dose, that dose will be skipped. If emesis occurs after TAK-659 ingestion, patients should not re-dose following emesis and should record the time of the emesis in their dosing diary. Patients should resume dosing at the next scheduled time with the prescribed dosage.

On clinic visit days, patients should be instructed to hold their dose until pre-dose assessments are performed. The timing of the visit should be planned so that the pre-dose PK draw occurs near the same time as the previous day's dosing. TAK-659 administration guidelines described above will still be followed on clinic days. On clinic days for PK determination, TAK-659 will be taken first and then Ixazomib. Patients should be instructed to return their empty blister packs to the clinic, rather than discarding them. Reconciliation will occur accordingly when the patient returns for their next cycle of take-home medication.

5.6.2 Ixazomib Administration

Ixazomib should be taken once a week on the same day and at approximately the same time for the escalating cycle. Ixazomib should be taken at least one hour before or at least two hours after food. The whole capsule should be swallowed with water. A total of approximately 8 ounces (240 mL) of water should be taken with the capsules. Patients should be instructed to store the medication between $+2^{\circ}\text{C}$ and $+30^{\circ}\text{C}$ (35.6°F - 86°F) for the duration of each cycle. Do not freeze Ixazomib or store above 30°C . Any extreme in temperature should be reported as an excursion and should be dealt with on a case-by-case basis.

The capsule should not be crushed, chewed or opened.

If an Ixazomib dose is delayed or missed, the dose should be taken only if the next scheduled dose is \geq 72 hours away. A missed dose should not be taken within 72 hours of the next scheduled dose. A double dose should not be taken to make up for the missed dose. If the patient vomits after taking a dose, the patient should not repeat the dose but should resume dosing at the time of the next scheduled dose. On clinic visit days, patients should be instructed to hold their dose until pre-dose assessments are performed. Ixazomib administration guidelines described above will still be followed on clinic days. On clinic days for PK determination, TAK-659 will be taken first and then Ixazomib.

5.7 Concomitant Medications

During the study, patients will be instructed not to take any additional medications (including over-the-counter products and supplements) without prior consultation with the investigator. At each visit, the investigator will ask the patient about any new medications he/she is taking or has taken while on study. All concomitant medications (defined as any medication given during the study) and significant nondrug therapies, including physical therapy and blood transfusions, should be recorded from signing of the informed consent form (ICF) through 30 days after the last dose of study drug or the start of subsequent antineoplastic therapy, whichever occurs first.

5.7.1 Allowed Concomitant Medications

All treatments considered necessary for a subject's welfare may be administered at the discretion of the treating physician in keeping with the community standards of medical care.

5.7.2 Prohibited Concomitant Medications

The following restrictions apply during the study:

- Any antineoplastic therapy other than TAK-659 is prohibited during the study (with the exception of hydroxyurea for the first 21 days of study drug treatment). This includes chronic use of corticosteroids at daily doses greater than the equivalent of 10 mg of prednisone as part of any anticancer treatment regimens. If alternative therapy is required for treatment of the patient's tumor, the patient should be removed from this study and the reason for removal recorded in the electronic case report form (eCRF).
- Radiation therapy (note that, in general, the requirement for local radiation therapy indicates disease progression). Palliative radiotherapy for local pain/symptom control in a preexisting nontarget lesion may be considered.
- Prophylactic use of myeloid growth factors (eg, granulocyte colony stimulating factor [G-CSF], granulocyte macrophage-colony stimulating factor [GM-CSF]) in Cycle 1 during dose escalation. Patients who experience severe and/or febrile neutropenia in Cycle 1 of dose escalation can be managed with growth factor support if needed in accordance with American Society of Clinical Oncology (ASCO) guidelines.
- Concurrent systemic administration of TAK-659 with inhibitors or inducers of P-gp or strong inhibitors or inducers of CYP3A should be avoided in this study. In vitro studies indicate that TAK-659 is a substrate for P-gp and that, among CYP isozymes, TAK-659 is preferentially metabolized by CYP3A4/5. Refer to the list below and in the Documents/Info tab of the EDC for a nonexhaustive list of medications, supplements, and food products that are inhibitors or inducers of P-gp or strong inhibitors or inducers of CYP3A based on the US FDA draft guidance for DDI studies.
 - Antifungals: itraconazole, ketoconazole, posaconazole, voriconazole.
 - Antibiotics: azithromycin, clarithromycin, erythromycin, telithromycin.
 - Antimycobacterials: rifabutin, rifampin, rifapentine.
 - Antiepileptics: carbamazepine, phenobarbital, phenytoin, primidone.
 - Antidepressant: nefazodone.
 - Immunosuppressant: cyclosporine.
 - Calcium channel blockers: diltiazem, felodipine, mibepradil, verapamil.
 - Antiarrhythmics: amiodarone, dronedarone, quinidine.
 - Antiplatelet: ticagrelor.
 - Antilipid: avasimibe.
 - Other cardiovascular: captopril, carvedilol, ranolazine.
 - Vasopressin antagonist: conivaptan.
 - Food/herbals/supplements: grapefruit-containing food and beverages, St. John's wort, quercetin.

If a patient experiences an AE on study and TAK-659 dosing is temporarily interrupted because of that AE, the medications listed above and in the Documents/Info tab of the EDC may be used for AE management if there is no appropriate alternative treatment available per the treating physician's judgment and the dosing is not concurrent with study drug. This situation should be evaluated by the sponsor investigator and patients should be closely monitored for potential toxicities.

Please note that strong CYP3A inducers should not be administered with Ixazomib. Among those are rifampin, rifapentine, rifabutin, carbamazepine, phenytoin, phenobarbital, and St. John's Wort.

Note that medications used to treat HIV or hepatitis C infection are not listed above because patients with known HIV infection or known hepatitis C infection are excluded from study participation.

